6.17 Post-Infusion / Pre-Discharge Assessment

The following clinical assessments will be performed prior to patient discharge from the acute care setting (preferably on the same day as the post-infusion, pre-discharge head CT that will be submitted to this study:

- **Glasgow coma scale score (GCS) [5 minutes]**
- **NIH Stroke Scale (NIHSS) [10 minutes]**

Adverse Event assessments will need to be performed daily by trained study personnel [See Section 8] for enrolled patients while patient is an inpatient. All adverse events (including hemorrhagic complications) will be documented, including all serious adverse events, adverse drug reactions, serious adverse drug reactions, unexpected adverse events, and unexpected adverse drug reactions. Any AE or SAEs such as bleeding, hemorrhagic, infarction, DVT, PE, or death that occur at any point from enrollment until the 90-day follow-up visit will be recorded in the EDC and will be available for the DSMB and in the final analysis of the study after study completion. SAEs must be reported to the CCC within 24 hours of the occurrence and AEs must be

reported to the DCC within 5 business days (7 calendar days) of the occurrence. These AE and SAEs should be reported to the study project manager. All adverse events will be handled according to good clinical practice. AEs will not be collected after the 90-day follow-up visit.

6.18 Discharge From Acute Care Setting

The patient will be discharged from the acute care setting per the normal SOC. The study patient is not expected to require any additional days of hospitalization or days in the intensive care unit by being enrolled in this trial. However, if the patient experiences a complication directly related to study drug infusion, there may be an increased length of stay as a result. Increased costs attributed to this unlikely event will be the burden of the patient and/or clinical site. The study's investigators and the University of Louisville (or any of its subsidiaries including the University of Louisville Research Foundation) will not provide indemnification to the clinical sites or patients against any increased expenses related to complications attributed to any patient's participation in this study. This will be listed as one of the risks of enrollment on the patient's informed consent document.

When a patient is clinically ready for discharge, they will be discharged from the hospital. Completion of the study drug infusion through the end of post-enrollment day 14 will not be an absolute requirement if the patient could otherwise be discharged. However, in our experience, it is rare for a patient with modified fisher grades 3 to be ready for discharge prior to post-enrollment day # 14. The total duration of the study drug infusion will be recorded, and any decreased length of study drug infusion because of early discharge will be noted but will not be considered a study deviation.

7. OUTPATIENT FOLLOW-UP VISITS

7.1 90 DAY (\pm 14 Days) FOLLOW-UP VISIT FROM DATE OF PROCEDURE

All patients in the study will be followed for the purposes of the study until the 90 day follow-up visit which will occur 90 days (\pm 14 days) after the SAH ictus. Thus, the primary data analysis date for the primary endpoint of the study will be after the last active patient enrolled in the trial reaches their 90-day follow-up and completes this visit.

Clinical, functional, social and cognitive evaluations are to be performed by properly trained study personnel. These evaluations are to be performed by personnel blinded to treatment allocation. Due to personnel time-off needs and vacations **we advise having at least two clinical research personnel designated and trained for these blinded assessments at each clinical site. This is above and beyond the need for a clinical research nurse / coordinator to manage the inpatient procedures.**

In the event that patients or families have already been informed of their treatment allocation, all patients and family members will be requested to not disclose this

information to the evaluators during this follow-up visit. Upon arrival at their follow-up visit, they will be given a letter reminding them not to disclose their treatment allocation.

The following evaluations will be administered during the follow-up visit: [Approximately 95 minutes-above and beyond the normal SOC]

- Montreal Cognitive Assessment (MoCA) [15 minutes]
- Modified Rankin Scale (mRS) via Rankin Focused Assessment tool (RFA) [10 minutes]
- Assessment of Return to Work Status [5 minutes]
- QOLIBRI-OS [5 minutes]
- NIH Stroke Scale (NIHSS) [10 minutes]
- Glasgow coma scale score (GCS) [5 minutes]
- CIS-f (fatigue scale) [5 minutes]
- Barthel Index [5 minutes]
- Trail Making Test Parts A&B [5 minutes]
- Lawton Instrumental Activities of Daily Living (Lawton-IADL) Score [10 minutes]
- Center for Epidemiologic Studies Depression Scale (CES-D) [5 minutes]
- Assessment for Adverse Events and Serious Adverse Events: [15 minutes]

8. MANAGEMENT OF ADVERSE EVENTS AND ADVERSE DRUG REACTIONS

Patient safety is of paramount importance in this trial and study personnel will be monitoring for adverse events throughout the trial. The Clinical Events Adjudication Committee (CEC) will review adverse events (AEs) according to the provisions of the ASTROH CEC Charter and will validate all serious adverse events (SAEs), adverse drug reactions (ADRs) and serious adverse drug reactions (SADRs). If the CEC identifies a dangerous or unexpected trend in SAEs, ADRs, or SADRs they will forward this information immediately to the chair of the DSMB.

8.1 DEFINITIONS

Adverse Drug Reaction (ADR): All noxious and unintended responses to a medicinal product related to any dose should be considered an adverse drug reaction. There must be a reasonable possibility that there is a causal relationship between the medicinal product and the adverse event.

- **Adverse Event (AE):** Any unfavorable and unintended sign (including laboratory findings), symptom or disease that occurs to a subject while enrolled in a clinical investigation. Medical conditions that exist at study enrollment are not considered an AE unless condition worsens after enrollment.

- **Serious Adverse Event (SAE) or Serious Adverse Drug Reaction (SADR):** Any untoward medical occurrence that at any dose:
 1. Results in death
 2. Is life threatening
 3. Requires inpatient hospitalization or prolongation of current hospitalization
 4. Results in persistent or significant disability/incapacity
 5. Results in a congenital abnormality or birth defect
 6. Requires a medical or surgical intervention to prevent a permanent impairment of a body function or permanent damage to a body structure.

- **Unanticipated Adverse Event (UAE) / Unexpected Adverse Drug Reaction (UADR)/or Other Unexpected Problems:** Unexpected (in terms of nature, severity, or frequency) means that:

1. The event and/or reaction was not previously described in the research procedures included in the protocol-related documents, such as the protocol, or consent document, or in other relevant sources of information, such as product labeling or package inserts.

OR

2. The event and/or reaction was not previously described given the characteristics of the participant or the participant population being studied such as natural progression of any underlying disease, disorder or condition of the participant experiencing the adverse event/reaction, and the participants predisposing risk factor profile for the adverse event/reaction.
- **Relatedness to study drug or participation in the research.** The site investigator will determine the causality of the AE or SAE (definitely not related, probably not related (unlikely), possibly related, probably related, definitely related). These designations will be adjudicated by the CEC.
 - **A problem** suggests that the research places subject or others at a greater risk of harm (physical, psychological, economic, or social harm) than was previously known or recognized.
 - **Unanticipated / unexpected problems involving risks to participants or others** are defined as meeting all of three of the following criteria:
 1. The event is unanticipated because it is not included in the currently approved research study documents, Investigator's Brochure, package insert, or study protocol or the event exceeds the described frequency or severity, or it is unexpected that it would occur given the study population described in the research. AND
 2. The event is definitely related, probably related or possibly related to procedures involved in the research. AND
 3. The event suggests that the research places the participants or others at a greater risk of harm than previously thought.

8.2 REPORTING OF ADVERSE EVENTS / REACTIONS

Adverse events are generally detected in two ways:

Clinical: Symptoms reported by the subject or signs detected on examination.

Ancillary testing: abnormalities of vital signs, laboratory tests, and other diagnostic procedures (other than outcome measures: the results of which are not being captured as AEs).

Assessment of Clinical Adverse Events

At each visit including the 90 day follow-up visit, the subject will be asked “Have you had any problems or symptoms since your last visit?” in order to determine the occurrence of adverse events. If the subject reports an adverse event, the Investigator will determine:

1. Type of event
2. Date of onset and resolution (duration)
3. Severity (mild, moderate, severe)
4. Seriousness (does the event meet the above definition for an SAE)
5. Causality, relation to investigational product and disease
6. Action taken regarding investigational product
7. Outcome

Relatedness of Adverse Event to Investigational Product

The relationship of the AE to the investigational product should be specified by the Site Investigator or the CEC, using the following definitions:

1. **Definitely Not Related:** Concomitant illness, accident or event with no reasonable association with treatment.
2. **Unlikely (probably not related):** The reaction has little or no temporal sequence from administration of the investigational product, and/or a more likely alternative etiology exists.
3. **Possibly Related:** The reaction follows a reasonably temporal sequence from administration of the investigational product and follows a known response pattern to the suspected investigational product; the reaction could have been produced by the investigational product or could have been produced by the subject’s clinical state or by other modes of therapy administered to the subject. (suspected ADR)
4. **Probably Related:** The reaction follows a reasonably temporal sequence from administration of investigational product; is confirmed by discontinuation of the investigational product or by re-challenge; and cannot be reasonably explained by the known characteristics of the subject’s clinical state. (suspected ADR)
5. **Definitely Related:** The reaction follows a reasonable temporal sequence from administration of investigational product; that follows a known or expected response pattern to the investigational product; and that is confirmed by improvement on stopping or reducing the dosage of the investigational product, and reappearance of the reaction on repeated exposure. (suspected ADR)

Recording of Adverse Events

All AEs and ADRs will be reported in the subjects’ medical record, and to the CEC by an online adverse event reporting system on the appropriate eCRF (REDCap). **Events**

that are both serious and unanticipated should be reported to the CEC within 24 hours once the site becomes aware of the event, in addition to following site-specific IRB procedures for adverse events/reactions. **All other SAE's, ADRs, and SADR's should be reported within 5 working days/7 calendar days** to the coordinating site once the site becomes aware of the event, in addition to following site-specific IRB procedures for internal reporting. Non-Serious AEs do not have a specific time reporting requirement.

If discernable at the time of completing the AE log, a specific disease or syndrome rather than individual associated signs and symptoms should be identified by the Site Investigator and recorded in the AE log. However, if an observed or reported sign, symptom, or clinically significant laboratory anomaly is not considered by the Site Investigator to be a component of a specific disease or syndrome, then it should be recorded as a separate AE on the AE log. The Site Investigator would typically identify "clinically significant laboratory abnormalities" as those that require intervention (AEs). Lab values that are out of the normal range that do not have any negative clinical effect or concern are not considered AEs.

Serious adverse events

Once a SAE is reported in REDCap the project manager monitoring the system will notify the Chair of the Clinical Events Committee as outlined in the CEC Charter. If the SAE is expected, then the SAE may be reviewed by the CEC at the next scheduled meeting time (at least quarterly). All unexpected SAEs will be addressed directly by the chair of the CEC within 10 business days of CCC notification and if the chair of the CEC feels that an impromptu full CEC meeting is necessary he will call that meeting within an additional 10 business days. The CEC may request further information if necessary. REDCap will store information on the AEs and their adjudication. The Project Manager will coordinate communications related to any adverse event in the study. If warranted, the CEC will notify the DSMB chair. The DSMB may suggest changes to the protocol or consent form to the Study Chair (PPI) as a consequence of adverse events. The DSMB has the right to halt the study at any time for reasons of patient safety.

Non-serious adverse events

Non-serious adverse events that are reported to or observed by the investigator or a member of his research team will be submitted in REDCap in a timely fashion (within 5 working days / 7 calendar days). The events will be presented in tabular form and given to the CEC chair on a quarterly basis or as requested. Local site investigators are also required to fulfill all reporting requirements of their local institutions.

The CCC will prepare aggregate reports of all adverse events (serious/not serious, expected/unexpected and relationship to the study drug) for the CEC and DSMB as needed per their charters.

A separate report detailing protocol compliance will also be available from the CCC for DSMB and/or site review every six months or as requested. The Study Leadership Team will then evaluate whether the protocol or informed consent document requires revision based on the reports.

8.3 EXPECTED (ANTICIPATED) RISKS

The following events have been identified as possible complications related to the diagnosis and treatment of aSAH including the coil embolization procedure as well as possible complications related to infusion of LDIVH. These events are anticipated as possible complications for patients enrolled in this trial but are not necessarily caused by the study intervention:

- Additional procedures
- Adrenal Hemorrhage / Insufficiency
- Alopecia
- Arrhythmia
- Aneurysm re-rupture
- Bruising
- Cardiac ischemia / infarction
- Cerebral ischemia
- Coagulopathy
- Cognitive deficits
- Coma
- Death
- Deep vein thrombosis
- Delayed neurological deficits
- Dissection or pseudoaneurysm
- Drug reaction (i.e., allergic) to contrast, antiplatelet medication, heparin
- Electrolyte imbalance
- Emboli (air, tissue, thrombus, or foreign body)
- Gangrene
- Gastrointestinal disturbance
- Headache
- Hematoma, pain, and/or infection of the surgical access site
- Hemorrhage
- Heparin induced thrombocytopenia
- Hepatic Injury
- Hormone imbalance
- Hypertension
- Hypotension
- Inability to resume gainful employment
- Infection
- Liver function test elevation
- Memory problems
- New neurological symptoms
- Ovarian hemorrhage
- Pain
- Paralysis
- Radiation burn or injury
- Rash or dermatitis
- Renal insufficiency/failure
- Respiratory distress/failure
- Retroperitoneal Hemorrhage
- Seizure
- Personality changes
- Pulmonary embolism
- Stroke
- Surgical intervention
- Syncope
- Transient ischemic attack (TIA)
- Thrombocytopenia
- Vasospasm
- Vessel occlusion
- Vessel perforation or rupture
- Vessel thrombosis

8.4 DEFINITION AND MANAGEMENT OF HEPARIN INDUCED THROMBOCYTOPENIA (HIT)

There are two types of HIT, Type I demonstrates a fall in platelets (100,000-150,000/ μ l) that returns to normal despite continued heparin exposure, it is asymptomatic and benign. Type II HIT is characterized by thrombocytopenia, a significant drop in platelets (<100,000/ μ l or <50% of baseline), increasing the risk for thrombotic events. Type II HIT occurs in ~0.3-5% of those treated with heparin, occurring typically 5-10 days after heparin exposure has begun, and 20-50% of these develop thrombotic complications.³⁷ The disruption of platelets indicative of HIT result in the formation of blood clots, thus symptoms of deep vein thrombosis (DVT), pulmonary embolism, heart attack, and stroke should be monitored for.³⁹ Symptoms of DVT include pain, tenderness, sudden swelling, skin discoloration, large visible veins, and skin that is warm to the touch.³⁹ Symptoms of pulmonary embolism include shortness of breath, dizziness, sharp chest pain, change in heart rate, anxiety, and sweating.³⁹ Skin changes to monitor for that may be associated with HIT include bruising/blackening around heparin injection sites, fingers and toes, and nipples that may become gangrenous.³⁹

Diagnostic and management process for this study to identify and treat HIT in study subjects should follow the site's own SOC. Some suggested management options are included below:

Management of HIT includes immediate discontinuation of the study drug infusion (UFH), any other heparin, including heparin coated catheters and heparin-containing flushes, and prompt administration of an alternative type of anticoagulant if clinically indicated (direct thrombin inhibitors, Factor Xa inhibitor, or Vitamin K antagonist) including, but not limited to argatroban, bivalirudin, lepirudin, hirudin, fondaparinux, and warfarin.^{38, 39} Platelet transfusions are contraindicated.³⁹

Suspicion of HIT type 2 will require stopping all heparin including the LDIVH infusion as above. If deemed necessary, suspected HIT type 2 may be confirmed via an immunoassay to detect antibodies to heparin/PF4. If it is later determined that the patient does not have HIT type 2, then the patient may resume their UFH treatments as indicated assuming acceptable platelet count levels per the judgment of the local investigator and / or the patient's attending physician.

8.5 DEFINITIONS AND MANAGEMENT OF BLEEDING / HEMORRHAGE EVENTS

We have chosen to follow formal guidelines set forth by the International Society of Thrombosis and Haemostasis for bleeding complications (Schulman S, et al. *J Thromb Haemost* 2005;3(4):692-694). The normal rate of major bleeding or clinically relevant non-major bleeding in aSAH patients with protected aneurysms is estimated at approximately 10-20% (EVD insertion/tract hemorrhages, femoral artery access complications, GI bleed, fall out of bed, nasopharyngeal feeding tube insertion, etc.).

Bleeding complications are defined as:

Any development of clinically relevant non major bleeding or major bleeding, as defined by the International Society of Thrombosis and Haemostasis (ISTH):**a) Major Bleeding (≥ 1 of the following in 24 hr time period):**

- i) Bleeding causing a fall in hemoglobin level of 2 g/dL or more, or leading to transfusion of two or more units of whole blood or red cells.
- ii) Symptomatic bleeding in a critical area or organ, such as intracranial, intraspinal, intraocular, retroperitoneal, intraarticular or pericardial, or intramuscular with compartment syndrome, and/or
- iii) Fatal bleeding

b) Clinically Relevant Non-Major Bleeding

- i) Acute or sub-acute clinically overt bleeding that does not satisfy the criteria for major bleeding and leads to physician-guided medical or surgical treatment for bleeding, or a change in antithrombotic therapy (including study drug) for bleeding.

c) Minor Bleeding

- i) All acute clinically overt bleeding events not meeting the criteria for either major bleeding or clinically relevant non-major bleeding are classified as minor bleeding.

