STUDY POPULATION	
Patients with a supratentorial aSAH secondary to a ruptured cerebral aneurysm that has been secured by endovascular coil embolization. Study subjects must score as a WFNS SAH grade ≤ 2 post-coiling with no significant aphasia at the time of enrollment and have a significant hemorrhage burden on the initial head computed tomographic (CT) scan that demonstrates a modified-Fisher grade 3, or grade 4 (with minimal intraparenchymal blood or IVH less than 25%.)

CLINICAL SITES	
Eight to ten designated clinical sites in the USA.

PLANNED ENROLLMENT	
88 patients (44 in each treatment allocation group; Approximately 5-6 patients per site per year average)

STUDY DURATION	
3 years [2 years enrollment; 3 months primary end-point follow-up visit; 3 months data analysis and reporting of results; 1-year follow-up visit secondary endpoint].

PRIMARY SAFETY ENDPOINT	
Rate of “Major Bleeding” or “Clinically Relevant Non-Major Bleeding” as defined by the International Society of Thrombosis and Haemostasis (ISTH) between the groups from enrollment until discharge from the acute inpatient setting.

SECONDARY SAFETY ENDPOINT	
Rate of Symptomatic Intracranial Hemorrhage between the two groups from enrollment until discharge from the acute inpatient setting. A symptomatic hemorrhage is defined as a 4-point or greater increase in the NIHSS or a decrease in the GCS by 2 or more points not explained by other causes.

ADDITIONAL PRESPECIFIED SAFETY OUTCOMES TO BE ANALYZED	
Rate of any new intracranial hemorrhage between the two groups from enrollment until discharge from the acute inpatient setting.
 
Rate of Serious Adverse Events (SAEs) between the two groups from enrollment until

the 90-day follow-up visit as reported by each site and adjudicated by an independent Clinical Events Adjudication Committee (CEC).

Rate of Type II Heparin Induced Thrombocytopenia (HIT) between the two groups from enrollment until the 90-day follow-up visit

Rate of DVT or PE between the two groups from enrollment until the 90-day follow-up visit

All cause and neurological mortality rates between the two groups from enrollment until the 90-day follow-up visit

PRIMARY CLINICAL EFFECT ENDPOINT

Mean Montreal Cognitive Assessment score (MoCA) at 90 (± 10) days post enrollment.

SECONDARY ENDPOINTS:

-PRIMARY BIOMARKER ENDPOINT

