All subjects will receive mechanical DVT prophylaxis with sequential compression devices and / or TED Stockings per the usual SOC at each site. Compliance with this prophylaxis will be documented. Control subjects should additionally receive chemical DVT prophylaxis (5000 units of heparin subcutaneously twice daily) which will be considered within the range of SOC for each clinical site. LDIVH subjects will not receive chemical DVT prophylaxis while actively receiving the study drug. All LDIVH subjects will receive chemical DVT prophylaxis following cessation of the study drug infusion until discharge or ambulatory per the usual SOC at each clinical site. Subjects will undergo DVT / PE screening / assessment per the usual SOC at their facility, although we recommend screening by weekly lower extremity venous duplex as aSAH patients have been reported to have deep venous thrombosis in up to 20% and this may serve as justification for modifying the local SOC. Other heparin drug(s) and heparin coated catheters and devices will not be utilized in this study except for treatment of an urgent or emergent medical condition requiring heparin (eg. DVT, PE, dissection) or as mentioned above, for chemical DVT prophylaxis.

All patients should be monitored for the development of heparin induced thrombocytopenia with daily CBCs (platelet counts) and per the guidelines of the American Society of Hematology:

https://www.google.com/url?sa=t&rct=j&q=&esrc=s&source=web&cd=4&ved=0CD0QFjADahUKEwjuqvWcil3HhAhWEJR4KHWNbCp4&url=http%3A%2F%2Fwww.hematology.org%2FClinicians%2FGuidelines-Quality%2FQuick-Ref%2F529.aspx&ei=rXK_Va6qNITLeOO2qfAJ&usq=AFQjCNF64VDAzo5VXjZEKiWau t2Xmep7iA&bvm=bv.99261572,d.dmo

Daily CBCs will be considered SOC for this study. Potential HIT cases will be evaluated per recommended protocols and SOC at each site based on the guidelines above. Any case (or suspected case) of type II heparin induced thrombocytopenia (Heparin Induced Thrombocytopenia and Thrombosis - HIT) will be treated by stopping the study drug infusion in LDIVH subjects and otherwise treated per the usual SOC at each clinical site. These events will be documented in the adverse event reporting system.

Routine clinical blood work will be drawn per each site's SOC.

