6.8 Initiation Of Study Drug, Standard Dose Escalation, And Duration Of Infusion

Once the patient has been randomized, if the patient has been randomized to the LDIVH treatment arm then the study drug will be initiated 12 ± 4 hours following the completion of the aneurysm treatment procedure. The LDIVH infusion will initiate at 8 u/kg/hr. The date and time of study drug initiation will be recorded in the CRF. The control group will not receive any study infusions.

The LDIVH infusion (LDIVH group only) will be initiated at 8 u/kg/hr. This rate of heparin infusion should typically be escalated twice to reach the standard goal infusion rate of 12 u/kg/hr. There should be 12 hours between each dose adjustment. This escalation should result in an increase of the rate by 2u/kg/hr to a minimum target of 12u/kg/hr. A follow-up aPTT should be checked 6 hours after dose initiation and each dose adjustment. The goal rate for the LDIVH group should be **at least** 12 u/kg/hr, however if the aPTT is still below the lower limits of the acceptable range, then 12 hours after the last dose escalation, the rate can be again increased by 1u/kg/hr beyond the minimum of 12 u/kg/hr. (Max infusion rate of 1800 units/hr). Again, LDIVH target is at least 12 u/kg/hr while maintaining an aPTT value within the range that correlates with an Anti-Xa value of 0.1-0.3 u/ml.

Example: Site A initiates LDIVH on Patient X weighing 80kg. Target aPTT for Site A is 40-60 seconds.

LDIVH gtt is initiated at 8 u/kg/hr (640 u/hr) and an aPTT is obtained 6 hours later. aPTT result 6 hours later is 42 seconds. (Even though aPTT was 42, you will always try to get to a minimum of 12 u/kg/hr minimum as long as aPTT is not above the upper goal [60 in this example])

Dose escalation needed.

12 hours after LDIVH initiation, Patient X will have the LDIVH rate increased to 10u/kg/hr (800 u/hr).

aPTT result 6 hours later is 38 seconds

Dose escalation needed.

LDIVH gtt is escalated 12 hours after last dose adjustment (approximately 6 hours after most recent aPTT value) to 12 u/kg/hr (960 u/hr).

aPTT result 6 hours later is 39 seconds

Dose escalation needed.

LDIVH gtt is escalated 12 hours after last escalation (6 hours after aPTT value) to 13u/kg/hr (1040 units/hr)

aPTT result 6 hours later is 42 seconds

No further dose adjustments needed for this patient at this time.

Routine aPTT checked 24 hours later and result is now 36 seconds and Patient X remains at 13u/kg/hr

Dose escalation needed.

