6.10.3 Bleeding Complications

Bleeding in all patients should be taken seriously and for those patients in the LDIVH treatment arm we recommend following the 2011 Clinical Practice Guide on Anticoagulant Dosing and Management of Anticoagulant-Associated Bleeding Complications in Adults; Presented by the American Society of Hematology, adapted in part from the: American College of Chest Physicians Evidence-Based Clinical Practice Guideline on Antithrombotic and Thrombolytic Therapy (8th Edition).

<https://www.google.com/url?sa=t&rct=j&q=&esrc=s&source=web&cd=1&ved=0CB8QFjAA&url=http%3A%2F%2Fwww.hematology.org%2FClinicians%2FGuidelines-Quality%2FQuick-Ref%2F525.aspx&ei=yE2PVYj1M8Ks->

[QGYyYHgDw&usg=AFQjCNHVwPINavcTi7zKKG74RuDEnxmHyqQ&bvm=bv.96783405,d.cWw](https://www.ncbi.nlm.nih.gov/pmc/articles/PMC6111111/)

The HASHTI principles of management of anticoagulant-associated bleeding are ideal and should be followed as the clinical scenario necessitates. Details on the HASHTI principles are included in the reference above.

HASHTI

1. **H**old further doses of anticoagulant
2. Consider **A**ntidote
3. **S**upportive treatment: volume resuscitation, inotropes as needed
4. Local or Surgical **H**emostatic measures: topical agents (aminocaproic acid, tranexamic acid)
5. **T**ransfusion (red cells, platelets, FFP as indicated)
6. **I**nvestigate for bleeding source

Patients who have Major Bleeding or Clinically Relevant Non-Major Bleeding and who are allocated to the LDIVH treatment arm should have the study drug infusion stopped immediately, an aPTT level checked, and consideration of administration of protamine sulfate if there is a life-threatening bleeding event. The UFH infusion can resume after the bleeding has been controlled and any aberrant coagulation parameters have been corrected based on the judgment of the local investigator (attending physician). The continuation of the LDIVH infusion should be delayed at least 12 hours after a major bleeding event and at least 6 hours after a moderate event. These are minimum restart times and the actual duration of time to wait after any bleeding event is at the discretion of the treating physician.

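### Bleeds that count only because antithrombotic therapy was changed depend on open-label decisions, and the hold and recording rules for them are written for LDIVH alone, so the primary safety endpoint can over-count LDIVH events

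*Protocol*

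**What the plan says.** **Definition (Section 8.5).** CRNM bleeding starts from "Acute or sub-acute clinically overt bleeding that does not satisfy the criteria for major bleeding". It is met if the bleed leads to physician-guided medical or surgical treatment, "or a change in antithrombotic therapy (including study drug) for bleeding". Beyond being overt there is no severity floor. Minor bleeding is the remainder: "All acute clinically overt bleeding events not meeting the criteria for either major bleeding" or CRNM bleeding.

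**Use (Section 1.1).** Major or CRNM bleeding, counted "from enrollment until discharge from the acute inpatient setting", is the primary safety endpoint. Study success also requires no significant between-group difference in it attributable to LDIVH.

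**Exposure.** Section 6.8: "The control group will not receive any study infusions". Section 3: "Control subjects should additionally receive chemical DVT prophylaxis (5000 units of heparin subcutaneously twice daily"; Section 6.12.5 repeats this. LDIVH patients have no chemical prophylaxis while the infusion runs.

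**Rules around a bleed.**
- Section 6.10.3 recommends its bleeding guide, whose first step is to hold the anticoagulant, for the LDIVH arm. Patients with Major or CRNM bleeding who are "allocated to the LDIVH treatment arm should have the study drug infusion stopped immediately".
- Section 9.1 keeps the infusion off after a new asymptomatic drain-related intracranial hemorrhage until a repeat CT is stable. It requires every LDIVH interruption to be documented with date, duration and reason, and an adverse event form when the hold is for hemorrhage. It has no matching text for control heparin.
- Section 5.4: treating staff are unblinded.

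**The concern.** One of the two routes into CRNM bleeding is a reaction to a bleed, not a property of it. The person who reacts knows the arm. On LDIVH there is a running infusion, a guide that begins with holding it, a rule for a prolonged hold after one kind of asymptomatic hemorrhage, and a form that captures the hold. In controls there is a twice-daily injection whose change also counts, but nothing says when a hold is expected or how it is recorded. Changes for the same bleed may therefore be both less frequent and less often captured in controls.

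At stake are the primary safety comparison and the success rule. Both could show an excess on LDIVH that partly reflects how staff respond to knowing the arm. The bias, if present, runs against LDIVH.

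**Working it through.** The protocol states no sample size, power or margin for the bleeding endpoint, so there is no figure of its own to reproduce. The check has two parts.

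**1. The same bleed in each arm** (overt, not major, needing no treatment)

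| Step | LDIVH | Control |
|---|---|---|
| Antithrombotic that can be changed | Infusion | Subcutaneous heparin |
| Does a change for bleeding make it CRNM? | Yes (8.5) | Yes (8.5) |
| Written guidance to hold | Yes (6.10.3, 9.1) | None found |
| Written rule to record the hold | Yes (9.1) | None found |
| Decision-maker blinded? | No (5.4) | No (5.4) |
| Class if nothing is changed | Minor | Minor |

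The definition is symmetric; the guidance and the recording are not.

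**2. Size of the effect**

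Inputs from the protocol:
- 44 patients per arm (Section 10.1).
- Chi-square test for categorical variables at the 5% level (Section 10.4). Sidedness for safety is not stated; two-sided is assumed, and only a significant excess on LDIVH is counted.
- Base rate b = 10-20%, the background rate in Section 8.5. That figure covers all Major or CRNM bleeding. Using it for bleeds that count whatever happens to antithrombotic therapy is an assumption.

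Inputs not in the protocol, assumed:
- m = 10-20% of the remaining patients have an otherwise-minor overt bleed.
- c = share of those bleeds for which antithrombotic therapy is changed, by arm.

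Formula for the counted rate in each arm: p = b + (1 − b) × m × c. Bleeding itself is the same in both arms; only c differs.

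Worked case, b = 0.10, m = 0.20, c = 0.50 on LDIVH and 0.10 in controls:
- LDIVH: 0.10 + 0.90 × 0.20 × 0.50 = 0.190
- Control: 0.10 + 0.90 × 0.20 × 0.10 = 0.118
- Excess: 0.072, with no true difference.

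The chance of a significant excess comes from summing the two binomial distributions (44 per arm) over all outcomes where the chi-square test is significant against LDIVH. In this case it is 0.159.

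Ranges over b = 10-20% and m = 10-20%:

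| Therapy changed, LDIVH vs control | Excess (points) | Chance of falsely significant harm |
|---|---|---|
| 50% vs 50% | 0 | about 2.7% |
| 50% vs 25% | 2.0-4.5 | about 4-9% |
| 50% vs 10% | 3.2-7.2 | about 6-16% |
| 75% vs 10% | 5.2-11.7 | about 9-31% |

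The low end of each range is m = 10%, b = 20%; the high end is m = 20%, b = 10%.

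**The case against.** **A reader might infer that the definition itself creates an excess, because only LDIVH patients have a study drug.** The text does not support that. The criterion is a change in any antithrombotic therapy, with study drug as one included case, and controls are on heparin. With equal change rates the excess is zero.

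**A reader might infer that Section 6.10.3 is circular, ordering a stop for any bleed and so turning it into an event.** Its stop instruction applies to bleeding already classed as Major or CRNM. The hold-first guide is to be followed as the clinical situation requires, and Section 9.1 has the attending investigator authorise a stop. What stands is that both texts address LDIVH only.

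**A reader might infer that any such excess fails the trial.** The success rule concerns differences attributable to LDIVH, and the events committee adjudicates relatedness. This softens the consequence but does not remove the problem. Section 3 does not list that committee among the blinded parties, and even a blinded adjudicator applying Section 8.5 must count a bleed for which therapy was changed.

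**The definition is taken from a recognised body, and dropping change-only bleeds could hide real harm.** This stands. Some heparin bleeds are controlled by stopping the drug and need nothing else. Removing them from the primary comparison would lose true events mainly from LDIVH and favour declaring it safe. That is why the primary definition should stay.

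**The size rests on assumed rates.** This also stands, and is why a range is shown, including equal change rates. LDIVH interruptions are already recorded with reasons, so the gap in recording is on the control side.

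**Conclusion.** The concern holds in a limited form. The change-in-therapy route is open to both arms, but it turns on unblinded decisions, and the hold guidance and hold recording are written for LDIVH alone. Following the protocol exactly can therefore count the same bleed more often on LDIVH. The direction depends on one condition: that therapy is changed, or the change recorded, more often on LDIVH for the same bleed. The protocol makes this plausible but gives no rate for it.

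Under the stated assumptions the false excess is 2.0 to 11.7 points, and the chance of falsely significant harm about 4% to 31%, against 2.7% with equal changes. These figures illustrate the possible size; they do not predict it. The point merits a correction to recording and analysis, not a new primary endpoint.

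**What to change.** 1. Keep the ISTH-based Major or CRNM definition as the primary safety endpoint.
2. For every bleed in both arms, record which CRNM criterion was met: medical or surgical treatment, change in antithrombotic therapy, or both.
3. Record changes to control heparin made for bleeding in the same way as LDIVH interruptions (date, duration, reason).
4. List by arm the bleeds that qualify only through a change in antithrombotic therapy.
5. Prespecify a sensitivity comparison of Major or medically or surgically treated bleeding, to be read beside the primary result when judging whether a difference is attributable to LDIVH.

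Cost: one CRF field, matching entries for control heparin, short wording in Sections 8.5 and 9.1, and one extra analysis. The sensitivity comparison may omit true heparin bleeds controlled by stopping the drug alone, so it should not replace the primary result. No change to the management of bleeding is proposed.
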